5.0 Treatment Program

5.1 Program Overview

The perioperative telemonitoring intervention includes four key components. The first component involves objective assessment of functional activity. Patients will receive a Vivofit 4 to wear for daily steps monitoring. Vivofit 4 is a commercially-available wristband pedometer (Garmin Company). It functions as a watch, but also can track activity level such as the number of steps taken. Vivofit 4 stores this data in the device. The device follows activity progress 24/7 and can stay on for more than a year without a battery change. It is waterproof and can be worn in the shower and while swimming.

The second component involves subjective, electronic assessment of PROs (symptoms, QOL). We will deploy the Aetonix A Touch Away™ digital engagement platform to remotely capture PROs in real-time. The A Touch Away™ platform is a HIPAA compliant, multi-faceted patient engagement system that remotely connects and conveys critical health information between patients and clinicians. The Aetonix application has been utilized in several clinical settings including monitoring patients with chronic obstructive pulmonary disease and congestive heart failure. Patients will use the application on a smart device (phone, tablet), home computer, or study tablet to complete ePROs and share with the surgical team.

The third component involves objective, remote assessment of physiologic patient generated health data (PGHD). Physiologic parameters of interest include pulse oximetry, temperature, blood pressure, heart rate, and weight assessed from the patient's home. Patients will be given a package that contains the following FDA-cleared devices: Nonin 3230 Bluetooth Smart Pulse Oximeters, FORA IR20 Ear Thermometer, A&D Medical Blood Pressure Monitor, and A&D Medical Weight Scale.

The fourth and final component involves a real-time, alert/feedback system based on pre-determined outcome/clinical thresholds. All PGHD and ePRO data captured via the devices and patient engagement application will be streamed in real-time to a dashboard accessible from any device for the surgical team to monitor. The dashboard provides a graphic visualization over time of all patients and their data to identify outcome trends, including onset, worsening/improving measures, and sporadic vs. consistent measures.

Figure 3 provides a graphic depiction of the perioperative telemonitoring care design.

[figure not shown]
[figure not shown]

Figure 3: Study Schema

Study Procedures

Before Surgery:

The study schema is presented in Figure 3. Patients will be recruited from the surgical clinics at COH's Duarte campus only. Research staff will explain the study purpose, answer questions, and obtain informed consent. Patients will be enrolled at least 3-7 days before surgery. Following informed consent, the study CRA will assist patients with identifying a patient-owned engagement device (smartphone, tablet, computer), and assist with setup and initial testing of the Aetonix application on the device of choice. For patients who do not have an engagement device or have poor connections at home, a study Samsung tablet will be provided for the duration of the study. In our previous experience, only about 1.5% of patients had no device or inadequate internet access.⁴⁸ All patients will be provided with a Vivofit 4 and instructions. The study CRA will setup the device for patients and conduct initial testing to insure successful data transmission. Patients will wear the Vivofit 4 on their non-dominant wrist. Patients in both

arms will receive a package with the Aetonix physiologic PGHD home monitoring devices described previously. The study CRA will provide instructions (both verbal and in writing) on device use. All patients will be instructed to complete baseline assessment (T1) of PGHD and ePROs while at home.

Following completion of baseline assessment, participants will be randomly assigned to either the telemonitoring or enhanced usual care arm, using stratified and blocked randomization. Strata will be defined by diagnosis (upper GI, colorectal, hepatobiliary) and surgical technique (minimally-invasive versus open). Variable block sizes will be used to maintain approximate balance and pre-assignment masking. A pre-established randomization log will be created by the project biostatistician. The study staff will communicate group assignments to the patients.

For patients assigned to the telemonitoring arm, the alert/feedback system, monitored by the CRN, will be initiated for each patient. The system will be triggered on the occurrence of predetermined threshold events for physiologic PGHDs and ePROs, as described previously. Patients assigned to the enhanced usual care arm will use the Aetonix application to report

physiologic PGHD and ePROs, but will be informed via electronic messages that their data will be used for research purposes only and would not be monitored. They will be instructed to follow the standard institutional procedure for reporting concerns and issues. This includes 1) contacting their surgical team if symptoms become severe and physical function worsens between clinic visits; and 2) use of the hospital call line to report problems between visits.

After Surgery and Before Hospital Discharge: After surgery, research staff will ensure that patients resume wearing the Vivofit 4 as soon as possible and no later than post-op day 2. Patients will complete repeat electronic PROs prior to discharge (T2). The surveys will take about 20 minutes to complete. Patients will be given instructions, prior to discharge, on when to use the home monitoring device.

After Hospital Discharge: After discharge, all patient-generated physiologic data and PRO assessments will be repeated day 2 (T2), day 7 (T3), day 14 (T4), and 30 days (T5) post-discharge. At day 30, patients randomized to the telemonitoring arm will participate in a brief exit interview. All patients will receive a \$25 remuneration after completion of the day 7, 14, and 30 assessments (\$75 per patient total).

All devices and loan study tablet will be returned upon study completion via postage-paid packages or in-person during a routine scheduled clinic visit. They will be cleaned with alcohol-based cleansers following standard protocols prior to re-use. Patients have the option of keeping the Vivofit 4 wristwatch or returning it to the research team. Patients will not be responsible for replacing lost study devices.

Feedback/Alert System and Thresholds: The following thresholds will be used to trigger the feedback and alert system monitored by the Research RNs.

1. Physiologic Health Parameters:
 - a. Weight – decrease in 2 kg since discharge or increase of 2 kg since discharge
 - b. Temperature - >38 C with heart rate >110 or systolic blood pressure <90 or >180 ; >38.3 C independent of other vital signs
 - c. Oxygen saturation - $<90\%$ oxygen saturation - Nurses should confirm that waveform data on heart rate and oxygen saturation are adequate (i.e not artifact)
 - d. Heart rate - >110 beats per minute (>120 if last heart rate at discharge was >100)
 - e. Blood pressure – systolic blood pressure <90 (<85 if last systolic blood pressure at discharge was <100) or >180 ; diastolic blood pressure ≥ 95 (low alert) and ≥ 100 (high alert).
 - f. Functional activity - daily steps of ≤ 1500 .
2. Patient-Reported Outcomes:
 - a. One or more symptoms rated 4 or greater (moderate-severe intensity)
 - b. One or more QOL questions rated moderate, severe, or unable to accomplish

Pathway for RN Triage and Management:

1. Patients will measure their vital signs once a day after discharge at 9 AM. Patients will have the option of measuring their vitals again at 3PM if they choose to
2. If RN identifies deviations from a priori thresholds, they will:

- i. Call the patient, and ask them to repeat all vital signs.
 - ii. Ask the patient if they are having: nausea, vomiting, fevers worsening pain, spreading redness around their incision, new or worsening drainage from their incision, chest pain, shortness of breath, difficulty breathing. Also ask if the patient is drinking at least 1.5 liters of fluid a day.
3. If vital signs on re-check are beyond threshold values but all the above patient-generated metrics are normal/negative, relay information to the on-call physician or health care provider for further determination of next course of action.
4. If vital signs on re-check are beyond threshold values and at least one of the patient-generated metrics is abnormal/positive, the patient should be evaluated within the next 24 hours. Relay information to the on-call physician or health care provider to determine exactly when/how evaluation should take place.
5. Evaluation within the next 24 hours may be:
 - i. Repeat vital signs in a pre-defined period of time to be reviewed by a health care provider
 - ii. Planned repeat phone conversation with the patient
 - iii. Clinic visit that day or the next business day
 - iv. Evaluation in the evaluation and treatment center or other urgent care/emergency department

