5.5 Supportive Care, Other Concomitant Therapy, Prohibited Medications

The study Clinical Research Nurses and CRAs will review participant's responses to all outcome measures and alert the attending surgeon if participants show risk of self-harm or other serious conditions. These participants will be referred to supportive care and social work as necessary after evaluation by the attending surgeon and/or other healthcare providers. Otherwise, there are no restrictions to the use of supportive care medications, other concomitant therapy and no prohibited medications.

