In order to protect PHI data the patients will be labelled as Subject # e.g. Patient001, Patient002. Only the PI on the study and CRAs and CRN will have access to Patient Identifiers. The CRNs will have the ability to document any response to the alerts of abnormal patient generated health data as a research progress note in EPIC. The PI and the CRAs and CRNs will have access to the Aetonix app on their COH provided devices. There will be no data integration into EPIC. The devices used to transmit the patient generated health data (blood pressure, weight, temperature, pulse oximetry and heart rate) do not store any of the data and are not linked to any patient identifiers. The vivofit4 used to capture the patient steps will require that patients sign up on the Garmin website and agree to the company terms of use. These will not be linked to clinical data in any way.

13.2.1.1 *Handling Missing Sessions and Data*

Subjects with missing items among dependent variables will be compared with subjects having non-missing items to determine whether there is any bias underlying the missing data (i.e., whether data are

missing at random or can be accounted for by other variables). We will consider multiple imputation (MI) for estimating missing responses and covariates, which can be done using PROC MI in the SAS 9.4 system of software for analysis. The estimates obtained across (10 to 20) multiply imputed data sets can be combined using proc MIANALYZE, which provides valid standard errors for making inferences using the missing at random assumption.

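### Does telling control patients that their data are not monitored conflict with the section 5.5 safety review in a way that needs a change to the plan?

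*Combined protocol and SAP*

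**What the plan says.** **Control arm, section 5.1 (Study Procedures, Before Surgery).** Patients in the enhanced usual care arm enter physiologic data and ePROs in the same Aetonix application as the other arm. They "will be informed via electronic messages that their data will be used for research purposes only and would not be monitored". The text then points them to the ordinary routes for raising a concern: the surgical team and the hospital call line.

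**Telemonitoring arm, section 5.1.** "For patients assigned to the telemonitoring arm, the alert/feedback system, monitored by the CRN, will be initiated for each patient". The threshold list opens with: "The following thresholds will be used to trigger the feedback and alert system monitored by the Research RNs".

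**Section 5.5 (Supportive Care).** CRAs and research nurses "will review participant's responses to all outcome measures and alert the attending surgeon if participants show risk of self-harm or other serious conditions". The next sentence reads: "These participants will be referred to supportive care and social work as necessary after evaluation by the attending surgeon and/or other healthcare providers". No arm is named.

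**Data access and records.** The description of the intervention's fourth component says: "The dashboard provides a graphic visualization over time of all patients and their data". Section 13.2.1 says: "The PI and the CRAs and CRNs will have access to the Aetonix app on their COH provided devices". It adds that the nurses "have the ability to document any response to the alerts of abnormal patient generated health data as a research progress note in EPIC". It also lists, among the stored data, care actions arising from the alert system and from nurse monitoring.

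**The concern.** Control patients are told that their data serve research alone and that nobody is watching them. Section 5.5 has staff look at every participant's answers and contact the surgeon in certain cases. Taken literally, one of two things seems to follow: the message to control patients is inaccurate, or a safety provision written for participants in general leaves out half of them.

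There is a statistical side too. The randomised contrast is between data that trigger a staff response and data that do not. If staff also act on control data, the arms could become more alike, and a reader would want to know how often that happened. Section 13.2.1 does not expressly name section 5.5 notifications, nor does it promise a count of them by arm.

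**Working it through.** The question is one of wording, so the main check is to set the texts side by side.

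**1. Who is affected.** Section 13.1.1 plans 160 patients with 1:1 allocation: 160 / 2 = 80 control patients receive the message.

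**2. What monitoring refers to.** Section 5.1 describes the alert system as monitored by the research nurse, for the telemonitoring arm. It then tells control patients that their data will not be monitored, and introduces the thresholds as belonging to the system that the research nurses monitor. In that sequence the message means that no one is watching thresholds on the patient's behalf. The instruction to use the surgical team or the call line fits that meaning.

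**3. Whether section 5.5 is the same activity.**

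| | Alert system (5.1) | Section 5.5 |
|---|---|---|
| Arm | Telemonitoring only | None named |
| Trigger | Listed cut-offs for vital signs, weight, steps, symptoms and QOL | Self-harm risk or another serious condition |
| Timing | Real time | Not stated |
| Response | Nurse call, repeat measurements, relay to a provider | Surgeon alerted, evaluation, referral if needed |

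The two differ in every row. A control patient can be outside the first and inside the second without either text being broken.

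**4. Dashboard and application access.** The dashboard sentence sits in the description of the intervention and may mean telemonitoring patients only. The statement on application access concerns who can open the data; access is not review. Neither shows that control data are watched.

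**5. Size.** The plan's own figure reproduces. A two-sample t-test with d = 0.5, two-sided alpha 0.05 and 64 per arm has power 0.801, and 128 / (1 − 0.20) = 160. To see what an effect on power would require, assume that a share p of control patients gained the whole intervention effect, so that d = 0.5 × (1 − p), and ignore the change in variance.

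| Assumed p | d | Power at 64 per arm | Share of 80 controls |
|---|---|---|---|
| 0.10 | 0.45 | 0.714 | 8 |
| 0.20 | 0.40 | 0.612 | 16 |
| 0.50 | 0.25 | 0.289 | 40 |

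The documents support no value of p. They give no rate for the section 5.5 trigger, and section 12.1.3 describes no instrument as having a self-harm item; the nearest is the anxiety/depression item of the EQ-5D-5L. The table shows only the scale of spill-over that would matter. It does not estimate what will happen.

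**6. What a wording change would do.** If section 5.5 covers both arms, stating so leaves p exactly where it was. The primary comparison, its test and its data stay the same.

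**The case for a change.** The best opposing case has three parts.

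First, the protocol names an arm when it means one, as it does for the alert system and the exit interview. Section 5.5 speaks only of participants and goes on to rules on concomitant treatment that are plainly study-wide. On that reading staff do look at control answers, and calling the data research-only is not accurate if they can lead to a surgeon alert and a referral. This stands, but it is narrow. It concerns one phrase in a paraphrase of a message whose text is not visible, and the consent pages are not available either.

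Second, section 5.5 neither defines a serious condition nor says when the review takes place, so two staff members might treat the same control-arm answer differently. The gap is real. It is the same for both arms, however, and no passage shows that it produces a wrong result.

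Third, section 5.5 notifications may go uncounted. This stands in part. Section 13.2.1 lists nurse monitoring in addition to the alert system as a source of stored care actions, which could cover what nurses do under section 5.5. CRAs share the review and are not named there. Counting notifications by arm within those data would be a reasonable descriptive extra, but its absence is not an error.

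**Conclusion.** This is a minor ambiguity and calls for no change to the plan. Sections 5.1 and 5.5 are compatible if monitoring means the threshold alert system that section 5.1 starts only in the telemonitoring arm. The visible text supports that reading but does not state it. What is left over is the research-only phrase, which sits awkwardly beside a conditional surgeon alert.

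The message reaches 80 of 160 planned patients. No effect on power or on the CCI comparison is shown, because the documents give no frequency for section 5.5 alerts.

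The conclusion rests on two assumptions: that the word is used consistently within section 5.1, and that the unseen message and consent text do not contradict section 5.5. Which patients section 5.5 should cover is a clinical matter on which this review takes no view. If the investigators revise either section for another reason, they can reconcile the wording then; the trial's conduct and conclusions do not depend on it.

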5.2 Planned Duration of Therapy

Study participation is planned for approximately 2-3 months. The timeframe covers before surgery, postop acute care, and up to 30 days post-discharge.

5.3 Criteria for Removal from Treatment

The only criterion for disenrollment is if participants desire to discontinue with study participation.

5.4 Subject Follow-Up

Subjects will be followed for approximately 2 months.

5.5 Supportive Care, Other Concomitant Therapy, Prohibited Medications

The study Clinical Research Nurses and CRAs will review participant's responses to all outcome measures and alert the attending surgeon if participants show risk of self-harm or other serious conditions. These participants will be referred to supportive care and social work as necessary after evaluation by the attending surgeon and/or other healthcare providers. Otherwise, there are no restrictions to the use of supportive care medications, other concomitant therapy and no prohibited medications.

5.6 Additional Studies

Not applicable.

5.6.1 Laboratory Studies

Not applicable.

5.7 Definition of Dose-Limiting Toxicity (DLT)

Not applicable.

6.0 Dose Delays/Modifications for Adverse Events

Not applicable.

7.0 Data and Safety Monitoring, Unanticipated Problems and Adverse Event Reporting

7.1 Data and Safety Monitoring

Definition of Risk Level

This is a low risk study, as defined in the [City of Hope Institutional Data and Safety Monitoring Plan \(DSMP\)](#), because it involves questionnaires assessing QOL and general functional status, use of pedometer, and assessment of physiologic health parameters that are routine vital signs during perioperative care. The study Principal Investigator is responsible for monitoring protocol conduct and reporting all reportable events to the City of Hope (COH) Data and Safety Monitoring Committee (DSMC) and Institutional Review Board (IRB) in accordance with the City of Hope Institutional Deviation policy, [and Clinical Research Adverse Event and Unanticipated Problem policy](#).

All reportable events occurring at external sites will be reported to the study Principal Investigator per City of Hope institutional policies, and per their local institutional policies, as applicable.

7.2 Monitoring and Personnel Responsible for Monitoring

Monitoring and Personnel Responsible for Monitoring

The Principal Investigator (PI) is responsible for monitoring protocol conduct and reporting to the City of Hope (COH) Data and Safety Monitoring Committee (DSMC) and Institutional Review Board (IRB) as indicated in the sections below.

7.3 Reporting of Unanticipated Problems and Adverse Events

Unanticipated Problems (UP) Involving Risks to Subjects or Others

An unanticipated problem is any incident, experience or outcome that meets all three of the following criteria:

1. Unexpected (in terms of nature, severity, or frequency) given the following: a) the research procedures that are described in the protocol-related documents such as the IRB approved research protocol, informed consent document or Investigator Brochure (IB); and b) the characteristics of the subject population being studied; **AND**
2. Related or possibly related to participation in the research (possibly related means there is a reasonable possibility that the incident, experience, or outcomes may have been caused by the procedures involved in the research); **AND**

3. Suggests that the research places participants or others at greater risk of harm (including physical, psychological, economic, or social harm) than previously known or recognized.

Any UP that occurs during the study conduct will be reported to the DSMC and IRB in accordance with the Clinical Research Protocol Deviation policy [policy effective date: 05/14/14] using the electronic submission system, iRIS.

Deviations

A deviation is a divergence from a specific element of a protocol and that occurred without prior IRB approval. Deviations from the approved protocol should be avoided, except when necessary to eliminate an immediate hazard to a research participant. A Corrective and Preventative Action (CAPA) plan should be developed by the study staff and implemented promptly to avoid similar issues in the future. All deviations from the protocol must be documented in study source documents and promptly reported to the DSMC and IRB.

Reporting Deviations

Investigators may deviate from the protocol to eliminate immediate hazards for the protection, safety, and well-being of the study subjects without prior IRB approval. For any such deviation, the PI will notify the DSMC and IRB, within 5 calendar days of its occurrence by electronic submission of a Deviation Notice via iRIS.

Single Subject Exception (SSE) Amendment Request

Deviations from the written protocol that are not done to eliminate an immediate hazard(s) for the protection, safety and well-being of study subjects but may increase risk and/or alter the protocol integrity require prior IRB approval. The deviation is submitted as a Single Subject Exception (SSE) amendment request. An IRB approved SSE does not need to be submitted as a protocol deviation to the DSMC. The SSE should be submitted according to the IRB guidelines and Clinical Research Protocol Deviation policy [policy effective date: 11/07/11] and submitted via iRIS.

A deviation that is not an SSE (i.e., discovered after the occurrence) must be reported to the COH DSMC and IRB according to the Clinical Research Protocol Deviation policy [policy effective date: 11/07/11] and submitted via iRIS.

